## Appendix 6 Expanded List of Allowed Concomitant Medications

- Prophylactic therapy for steroid-induced bone loss (calcium with Vitamin D and/or a bisphosphonate).
- Low dose aspirin is allowed for cardiovascular prophylaxis.
- Minor GI AEs (such as nausea, vomiting and diarrhea) may be treated symptomatically (e.g., with loperamide for diarrhea or standard anti-emetics such as metoclopramide or domperidone for nausea and vomiting). Proton pump inhibitors or ranitidine are permitted for dyspepsia or gastric protection. Magnesium or aluminum containing antacids may be used, but should not be taken at the same time as study treatment; such antacids, if required, should be taken either 1 hour before or 2 hours after study treatment.
- Amphotericin or oral nystatin are permitted as infective prophylaxis against fungal infections, and low-dose sulfamethoxazole/trimethoprim is permitted as prophylaxis against *Pneumocystis carinii pneumonia*.
- Granulocyte colony stimulating factor is allowed to manage neutropenia in the presence of major infection (i.e., infections requiring IV antibiotics).
- Oral or IV iron preparations for iron deficiency and/or anemia.
- Erythropoietin is permitted for treatment of severe anemia (hemoglobin <10 mg/dL).
- Cytomegalovirus prophylaxis is permitted for example with oral valganciclovir.
- Acute intermittent administration of NSAIDs for not greater than 7 consecutive days is permitted.
- Lipid-lowering therapies (e.g., statins) will be used as clinically indicated.
- Antimalarials should be prescribed when clinically indicated.
- Angiotensin-converting enzyme inhibitors, ARBs, and aliskerin and other therapies are recommended, as per standard guidelines but if used their dose must be stable throughout the study. In addition subjects must be on a stable dose of ACE inhibitors or ARBs for 4 weeks prior to enrollment.
- In the case of uncontrolled hypertension (systolic BP >165 mmHg or diastolic >105 mmHg on 2 successive measurements), the addition of a diuretic or calcium channel blocker only are permitted, together with dose decreases or

[figure not shown]
interruption of study treatment per the instructions in Section 7.9, [Increased Blood Pressure](#).

[figure not shown]

[figure not shown]

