### 7.8.1 Prohibited Medications

The same medications prohibited in the AURORA 1 study will be prohibited in this study.

The following medications cannot be taken during the study:

- IV corticosteroids unless approved by the Medical Monitor
- Enteric-coated oral corticosteroids during the study are not allowed. No other use of non-enteric coated oral corticosteroids, other than administration required as per protocol, is allowed
- IV immunoglobulin treatment
- Cyclophosphamide
- Cholestyramine or other drugs that may interfere with enterohepatic recirculation of MMF
- Initiation of new treatment or change in dosage of ARBs and/or ACE inhibitors
- CNIs (e.g., cyclosporine and tacrolimus)
- Immunosuppression biologic agents (e.g., abatacept, belimumab, infliximab, adalimumab, etanercept, or rituximab)
- Vaccines using live organisms, viral or bacterial
- MMF dose other than 2 g/day without prior discussion with the Medical Monitor
- Concomitant therapy with other immunosuppressants after consent, other than MMF administered per protocol
- AZA or mycophenolate sodium
- Ketoconazole or rifampin
- Concomitant use of other CYP3A4/5 inhibitors and inducers should be discussed with the Medical Monitor

[Appendix 7](#) contains a summary of additional treatment and food restrictions.

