## Appendix 7 Summary of Treatment and Food Restrictions

[figure not shown]
Treatment	During Treatment	Reason
Immunosuppressants other than those allowed by protocol	Prohibited	Interferes with study efficacy endpoints
Aminoglycosides Amphotericin B Melphalan Ketoconazole Rifampin	Prohibited	May potentiate toxicity
NSAIDs chronic dosing (>7 consecutive days)	Prohibited	May potentiate nephrotoxicity
P-gp substrates	To be monitored	Drug-drug interaction
P-gp inhibitors	To be discussed with Medical Monitor	Drug-drug interaction
Androgenic steroids Cimetidine Fluconazole, itraconazole Macrolide antibiotics (azithromycin, clarithromycin, erythromycin) Metoclopramide Barbiturates and derivatives Carbamazepine Octreotide acetate Phenytoin Sulfadimidine (intravenous) Theophylline	To be discussed with Medical Monitor	Drugs interfering with Orelvo metabolism
ACE inhibitors and ARBs	Change or commencement prohibited	Interfere with primary endpoint assessment
Foods Grapefruit and grapefruit juice	Prohibited	May affect the metabolism of Orelvo

[figure not shown]
Abbreviations: ACE = Angiotensin converting enzyme; ARB = Angiotensin receptor blocker; NSAID = Non-steroidal anti-inflammatory drug; Pgp- = P-glycoprotein.

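### Appendix 6 permits amphotericin for antifungal prophylaxis, Appendix 7 prohibits amphotericin B, and no sentence in the protocol says which entry governs

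*Protocol*

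**What the plan says.** Appendix 6 is the expanded list of allowed concomitant medications. Its prophylaxis entry reads "Amphotericin or oral nystatin are permitted as infective prophylaxis against fungal infections". Section 7.8.2 refers investigators to this appendix for treatments they may use on their own medical judgment.

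Appendix 7 is the summary of treatment and food restrictions. One row groups "Aminoglycosides Amphotericin B Melphalan Ketoconazole Rifampin". The whole row is marked as prohibited during treatment, and the reason given is possible potentiation of toxicity. The row carries no route and no exception for prophylaxis.

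Three parts of the body text bear on how the two lists relate:

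- Section 7.8.1 begins "The same medications prohibited in the AURORA 1 study will be prohibited in this study". It then gives its own list, which does not name amphotericin, and ends by describing Appendix 7 as additional restrictions.
- Section 7.8.2 cites both appendices in one paragraph. It asks for Medical Monitor verification of treatments that are not in Appendix 6.
- The opening of Section 7.8 requires discussion with the Medical Monitor, with documentation, for medication classes that the section does not go on to mention and that could interfere with evaluation of study treatment.

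The SAP does not address the point.

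**The concern.** The two appendices are both working instructions to sites, and as written they give opposite answers for the same drug. A site that looks only at Appendix 6 has permission to use amphotericin. A site that looks at Appendix 7 has a prohibition, with toxicity as the reason. The subjects have lupus nephritis and may be taking a calcineurin inhibitor, so a restriction based on toxicity should not be easy to miss.

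The situation could arise in practice. Appendix 7 prohibits ketoconazole and requires Medical Monitor discussion for fluconazole and itraconazole. That leaves amphotericin and oral nystatin as the two antifungals that Appendix 6 names and permits with no such step.

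What is at stake is site conduct and subject safety. A secondary matter is record-keeping: the same use could be treated as permitted under one appendix and as a deviation under the other.

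**Working it through.** No arithmetic applies beyond counting entries. The check sets the texts side by side.

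| Feature | Appendix 6 | Appendix 7 |
|---|---|---|
| Name used | Amphotericin | Amphotericin B |
| Status | Permitted | Prohibited during treatment |
| Purpose or reason | Antifungal prophylaxis | Possible added toxicity |
| Route stated | None | None |
| Exception stated | None | None |

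**Same drug.** The protocol draws no distinction between the two names, so they are taken to be the same drug. This is an assumption.

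**Route.** In the Appendix 6 entry the word *oral* stands after *or* and directly before nystatin. Applying it to amphotericin means reading it backwards across the conjunction, which the wording does not support. Count: 2 amphotericin entries, of which 0 state a route.

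**What a reconciled pair looks like.** For NSAIDs, Appendix 6 says "Acute intermittent administration of NSAIDs for not greater than 7 consecutive days is permitted", and Appendix 7 prohibits dosing beyond 7 consecutive days. No duration falls under both rules. The amphotericin entries have no such boundary.

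**Precedence.** Sections 7.8, 7.8.1 and 7.8.2 contain no sentence ranking the appendices. The description of Appendix 7 as additional restrictions, and the pointer to it at the end of Section 7.8.2, lean towards the prohibition. Section 7.8.2 equally presents Appendix 6 as a list the investigator may use. The list in Section 7.8.1 is silent on amphotericin.

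**Medical Monitor checks.** There are two to test.

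- Section 7.8.2: it covers treatments absent from Appendix 6. Amphotericin is in Appendix 6, so this check is not triggered.
- Opening of Section 7.8: it covers classes not mentioned below it. If that means the lists in 7.8.1 and 7.8.2 alone, amphotericin is unmentioned and the rule could apply. If it includes the appendices those sections cite, amphotericin is mentioned, and permitted in one of them, so the rule does not apply. The rule is therefore not clearly triggered.

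**Other overlap.** Metoclopramide is allowed in Appendix 6 as a standard anti-emetic and needs Medical Monitor discussion under Appendix 7. This is the same kind of mismatch in a milder form, because one status is a condition and not a ban.

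**The case against.** The strongest reply is that Appendix 7 works as a layer over Appendix 6. Section 7.8.1 calls its restrictions additional, Section 7.8.2 sends the reader to both lists, and metoclopramide, ACE inhibitors and ARBs also appear in both, with the tighter terms in Appendix 7. On that reading the stricter entry governs and nobody is led to give a prohibited drug. This has weight and is the better guess at how the lists relate. It remains a guess, because no sentence states it, and it would leave the amphotericin permission with nothing to permit.

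A second reply is that the sponsor meant local use allowed and systemic use barred. That is plausible, but the documents do not say so. The AURORA 1 prohibited list that Section 7.8.1 carries over is not among these documents and might settle it. Figures are missing near both entries in the text reviewed, so a lost qualifier is possible, though none is visible.

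A third reply is that safeguards exist. All concomitant treatment is recorded (Section 7.8). Creatinine and eGFR are assessed at every visit (Section 7.6.1), and contributing factors are considered when a confirmed eGFR fall meets the Section 7.6.1.1 criteria. These limit the consequence but do not remove the conflict.

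A reader might also infer more than the text supports:

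- *That the appendices habitually state routes, so the silence on amphotericin is telling.* Only nystatin and sulfadimidine carry a real route limit. The iron entry, "Oral or IV iron preparations for iron deficiency and/or anemia", names both routes, and valganciclovir is given only as an example. Many Appendix 6 entries state no route.
- *That no Medical Monitor check could apply.* The rule opening Section 7.8 might apply; it is only unclear.
- *That eligibility is affected.* Exclusion criterion 2 (Section 5.3) refers to items listed in Section 7.8. The body of that section does not name amphotericin and cites both appendices, so this adds little.
- *That toxicity would differ by arm or bias a result.* The documents give no frequency of use and no basis for such a claim.

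**Conclusion.** The inconsistency is real and minor. One drug is permitted in one appendix and prohibited in the other, with no route in either entry and no rule of precedence; a second drug, metoclopramide, has a milder mismatch. The text leans towards the prohibition without saying that it governs. A site following Appendix 6 as written could therefore give a drug that Appendix 7 bars on toxicity grounds, and neither Medical Monitor check is certain to intervene.

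This is a correction to site instructions for safety reasons. No endpoint, estimate or planned analysis changes. How often amphotericin would be used is unknown.

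The conclusion assumes that the two names denote the same drug and that no qualifier was lost with the missing figures. Confidence is medium, chiefly because the AURORA 1 list has not been seen. The local-versus-systemic explanation is an inference, so the remedy should not depend on it unless the sponsor confirms it.

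**What to change.** 1. In Appendix 7, state that systemic amphotericin B is prohibited.
2. In Appendix 6, choose one of two wordings after checking the AURORA 1 prohibited list. If the sponsor confirms that local use was intended, limit amphotericin to local use (non-absorbed oral or topical). If not, delete amphotericin and leave oral nystatin.
3. Add one sentence, in Section 7.8.2 or at the head of Appendix 6, that Appendix 7 prevails where the two lists overlap. This also settles metoclopramide in favour of Medical Monitor discussion.

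Step 3 should not be made alone. With the Appendix 7 entry left unqualified, it would cancel any local-use permission the sponsor wished to keep.

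The cost is a few words in one entry of each appendix and one sentence, at the next protocol amendment. Data collection, the SAP and the analyses stay as they are.

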## 7.9 Increased Blood Pressure

For all subjects, the target systolic pressure is  $\leq 130$  mmHg and the target diastolic pressure is  $\leq 80$  mmHg. Investigators should use all means possible permitted in the protocol to maintain the BP within these limits. If no further adjustment of antihypertensive therapy is possible, the subject should be discussed with the Medical Monitor.

If on any study day, systolic BP is  $>165$  mmHg or diastolic BP is  $>105$  mmHg and is associated with symptoms of hypertension (i.e., persistent headache, altered mental status, shortness of breath, chest pain consistent with angina pectoris, symptoms of heart failure, evidence of renal insufficiency of new onset, evidence of hypertensive retinal injury [hemorrhages, papilledema]), study treatment should be withheld, the Medical Monitor contacted, and the subject treated as per Investigator local practices and best judgment. The subject will continue with all study visits per the [Schedule of Events](#). Study treatment must not be reintroduced without prior discussion with the Medical Monitor.

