#### 9.1.3.1 Blood Pressure Management

BP and heart rate (HR) will be measured with the subject in a sitting position after 5 minutes of rest. The procedure for standardized measurement of BP is detailed in [Appendix 2](#).

If the BP measure is confirmed to be >130/80 mmHg (i.e., by the mean of the second and third repeats of 3 readings), the subject's BP will be managed per local practice. If the BP remains uncontrolled with the maximal doses of first and secondline- antihypertensive therapies referenced in [Appendix 1](#), then the Investigator should contact the Medical Monitor to consider dose adjustment of the study treatment. See Section 7.9, [Increased Blood Pressure](#) for management of increased BP.

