## Appendix 1 Drug Therapy for the Treatment of Hypertension

Antihypertensive drug therapy for subjects who develop hypertension while on study treatment may include the following:

- Dihydropyridine calcium channel blockers (e.g., amlodipine, nifedipine)
- Alpha-1-adrenergic blocking agents (e.g., doxazosin)
- Alpha-beta-blockers (e.g., carvedilol, labetalol)
- Thiazide diuretics (e.g., chlorthalidone or hydrochlorothiazide)

Excluded Drugs: While the ARBs and ACE inhibitors may also be effective in CNI-associated hypertension, their dose adjustment or commencement is not permitted in this trial (see Section 7.8.1, [Prohibited Medications](#)).

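### At BP above 165 or 105 mmHg twice, Protocol Appendix 6 bars adding the labetalol that Appendix 1 names as second line, and its pointer to Section 7.9 reaches no dose-decrease rule

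*Protocol*

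**What the plan says.** Four parts of the protocol govern raised blood pressure.

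- **Appendix 6**, uncontrolled hypertension bullet. The trigger is systolic BP above 165 or diastolic above 105 mmHg on 2 successive measurements, with no symptom condition. At that point "the addition of a diuretic or calcium channel blocker only are permitted, together with dose decreases or" "interruption of study treatment per the instructions in Section 7.9".
- **Section 7.9.** It sets a target of at most 130/80 mmHg and adds: "Investigators should use all means possible permitted in the protocol to maintain the BP within these limits". When drug options run out: "If no further adjustment of antihypertensive therapy is possible, the subject should be discussed with the Medical Monitor". Its one action on study drug, withholding, applies when "systolic BP is $>165$ mmHg or diastolic BP is $>105$ mmHg and is associated with symptoms of hypertension". Such subjects are then treated by local practice and the investigator's judgement.
- **Section 9.1.3.1.** Once BP is confirmed above 130/80 mmHg, the subject's "BP will be managed per local practice". If BP stays uncontrolled on maximal doses of the first- and second-line drugs in Appendix 1, "then the Investigator should contact the Medical Monitor to consider dose adjustment of the study treatment".
- **Appendix 1.** For subjects who develop hypertension on study treatment, it lists four classes: dihydropyridine calcium channel blockers, alpha-1 blockers, alpha-beta blockers and thiazide diuretics. Its stepped regimen gives labetalol as the only second-line drug, to be added after a partial response. A closing note allows reduction of the study dose, or discontinuation, if BP is still uncontrolled.

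**The concern.** Appendix 6 restricts add-on drugs at exactly the BP level where more treatment is likely to be needed, and the drug it shuts out is the one Appendix 1 offers as the next step. No text says which appendix prevails. Since Section 7.9 tells investigators to use every means the protocol permits, the governing list decides what may be given. Read literally, adding labetalol for a partial responder above the threshold follows one appendix and breaches the other, and Section 17.1 does not permit waivers.

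The cross-reference is a second fault. An investigator who follows it from Appendix 6 to Section 7.9 for an asymptomatic subject finds no instruction on decreasing the dose.

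Blood pressure matters for this drug. Section 1.2.5 reports more treatment-emergent hypertension on voclosporin than on placebo, and Section 2.1 names BP as one of the safety concerns for which the protocol provides dose management. What is at stake is a clear instruction to the site: two rules that disagree can cause delay or an avoidable protocol deviation.

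**Working it through.** No formula applies and the plan gives no figure to reproduce. The check sets the rules side by side.

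**1. Which drugs may be added above 165 or 105 mmHg twice?**

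| Appendix 1 class | Addable under Appendix 1 | Addable under Appendix 6 |
|---|---|---|
| Dihydropyridine calcium channel blocker | yes | yes |
| Thiazide diuretic | yes | yes |
| Alpha-1 blocker | yes | no |
| Alpha-beta blocker | yes | no |

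Classes excluded by Appendix 6: 4 − 2 = 2.

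Named drugs in the stepped regimen:
- First line: amlodipine, nifedipine XL, chlorthalidone and hydrochlorothiazide. Addable under Appendix 6: 4 of 4.
- Second line: labetalol. Addable under Appendix 6: 0 of 1.
- Together: 4 of 5.

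These are counts of list entries, not of subjects. Appendix 6 names its two classes without subclass, and Appendix 1 presents its list as what therapy may include, so neither list is closed within a class.

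**2. Do the two rules apply to the same subject?** Yes. Appendix 1 covers any subject who develops hypertension on study treatment, and neither it nor Section 9.1.3.1 sets an upper BP limit. The Appendix 6 trigger lies inside that range.

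**3. Where does the conflict bite?** Take an asymptomatic subject on amlodipine 10 mg daily with a partial response, not on labetalol, whose systolic BP exceeds 165 mmHg on 2 successive measurements. Appendix 1 says labetalol may be added; Appendix 6 says only a diuretic or calcium channel blocker may be. Section 9.1.3.1 raises study-dose adjustment after maximal first- and second-line therapy, a sequence this subject cannot literally complete under Appendix 6.

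The conflict is weaker or absent in two other cases. If labetalol is already in use, Appendix 6 limits only additions, so titration is open. If symptoms are present, Section 7.9 allows treatment by local practice and judgement and sets no class limit.

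**4. What does the Section 7.9 pointer reach?**

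| Instruction on study drug | Section 7.9 | Elsewhere |
|---|---|---|
| Withhold, symptomatic | 1 rule | – |
| Withhold, asymptomatic | none | Section 7.2.2.1 allows holding at the investigator's discretion |
| Decrease dose for BP | none | Appendix 1 note; Section 9.1.3.1 (adjustment, via Medical Monitor) |
| Reduce or interrupt for other disturbances | none | Sections 7.2.2.1 and 7.6 |

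The pointer therefore reaches an interruption rule for symptomatic subjects but no dose-decrease rule. The provisions exist; Appendix 6 does not point to them.

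**The case against.** The case on the other side is substantial, and most of it stands as a limit on scope.

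- **Appendix 6 is not a closed list.** Section 7.8.2 says unlisted treatments may be acceptable once verified with the Medical Monitor. That gives a documented route to labetalol, but it does not plainly override an express restriction to two classes. At best it adds a consultation to a step Appendix 1 already recommends.
- **Section 9.1.3.1, in the body of the protocol, relies on Appendix 1**, which suggests that Appendix 1 should govern. That is reasonable, but nothing says so, and one could equally argue that the narrower rule for severe readings was deliberate.
- **The situation is narrow.** Management starts above 130/80 mmHg, so labetalol may already be in use before the threshold is reached. This stands.
- **Section 17.1 exempts deviations needed to remove an immediate hazard.** This stands too. A reader might infer from the ban on waivers that an investigator facing dangerous BP is barred from giving labetalol; the exemption defeats that reading. It helps less with a routine asymptomatic partial responder.

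A reader might also infer that such a subject is left with no action on study drug. The documents do not support this. The Appendix 6 bullet itself permits decreases or interruption, Sections 7.2.2.1 and 7.6 allow holding or reducing, the Appendix 1 note allows reduction or discontinuation, and Sections 7.9 and 9.1.3.1 lead to the Medical Monitor.

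**Conclusion.** The point holds as an internal inconsistency in a participant-safety instruction. Appendix 6 and Appendix 1 disagree on what may be added above 165 or 105 mmHg twice, most clearly for asymptomatic subjects not yet on labetalol, and the Appendix 6 cross-reference to Section 7.9 is incomplete. The consequence is conflicting guidance with possible delay or an avoidable deviation, not an unmanaged subject.

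Its size in subjects cannot be derived, because the documents do not say how often such readings occur or how many subjects would already be on labetalol. The conclusion rests on reading the Appendix 6 restriction literally and on the absence of any order of precedence between the appendices.

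Since hypertension is a safety outcome, a reader might infer that the adverse event comparison is compromised. The documents do not support that: the rules are the same in both blinded arms, and no endpoint definition or planned analysis depends on which list is followed. The documents also do not show whether the narrower list was intended, so adopting the wider one needs the sponsor's clinical agreement. The correction is worth making but minor.

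**What to change.** Replace the Appendix 6 bullet with wording to this effect:

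> If hypertension is uncontrolled (systolic BP above 165 mmHg or diastolic BP above 105 mmHg on 2 successive measurements), a diuretic, a calcium channel blocker or any other agent listed in Appendix 1 may be added, subject to Appendix 7. Starting or changing an ACE inhibitor or ARB remains prohibited (Section 7.8.1). Study treatment may be reduced or interrupted at the Investigator's discretion, and the Medical Monitor should be contacted (see Section 9.1.3.1 and Appendix 1). If symptoms of hypertension are present, study treatment should be withheld and the Medical Monitor contacted per Section 7.9.

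This keeps every add-on now allowed and admits the Appendix 1 agents. It retains the direct permission to decrease or interrupt study drug in asymptomatic subjects without making that wait on the Medical Monitor, and it sends the reader to the sections that deal with dose changes.

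The cost is one bullet in a protocol amendment, with IRB/IEC approval before implementation under Section 17.1. It can be bundled with another amendment and needs no new data collection and no change to the SAP.
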